Safety summaries (tables, figures) on the Safety set (respectively on the Switch Analysis Set) include only data from the on-treatment (resp. on-switched treatment) period with the exception of baseline data which will also be summarized where appropriate (e.g. change from baseline summaries). In particular, summary tables for adverse events (AEs) will summarize only on-treatment (resp. on-switched treatment) events, with a start date during the on-treatment (resp. on-switched treatment) period (**treatment-emergent** AEs) (resp. switched-treatment-emergent AEs). In addition, a separate summary for death including on-treatment and post-treatment deaths will be provided.

However, all safety data (including those from the pre-treatment, post-treatment and post-switched treatment period) will be listed and flagged as appropriate.

Efficacy summaries on the FAS (apart from OS and PFS) include data from baseline up to either the last assessment on or before the EoT visit or before or on treatment failure, whichever is the earliest.

Efficacy summaries on the Switch Analysis Set include data from baseline_switch up to the last assessment on or before the S-EoT visit or before or on treatment failure during the switched treatment period, whichever is the earliest.

The efficacy assessments collected post-treatment failure, post-EoT or post S-EoT visit are not included in any efficacy analyses (except for OS and PFS analyses). However, they will be listed and flagged as appropriate.

Windows for multiple assessments

Data such as molecular response, cytogenetic response collected over time (including unscheduled visits) will be summarized by scheduled time point. As patients do not always adhere to the visit schedule, visits will be remapped according to visit windows defined in Tables 2-1 to Table 2-4 of this document to enable by-visit analysis. Only those protocol-defined visits will have the visit window defined. Each assessment (including the end of treatment assessment), either scheduled or unscheduled, will have a mapped visit assigned, as long as study day is available, according to the defined visit window up to the date with data included.

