2.7.1 Secondary endpoints

2.7.1.1 Molecular response

MMR rates at all scheduled data collection time points, i.e., the protocol-planned visits except for 24 weeks and 96 weeks which are already covered by primary and key secondary endpoints. Such rates are defined as the proportion of patients with MMR at the respective time points.

MMR rates by all scheduled data collection time points, i.e., the protocol-planned visits. These are cumulative MMR rates by time points and are defined as the proportion of patients who achieve MMR at or before specified visits, i.e. if a patient achieves an MMR but then loses it before or at a specific visit, he/she will still be classed as achieving MMR by that specific time point.

Molecular response category at specific time points, i.e., the protocol-planned visits. Categories of molecular response are defined in Appendix.

Molecular response category by specific time points, i.e., the protocol-planned visits. This is defined as the best (lowest) molecular response category up to the specific time points.

Time to MMR (in weeks) is defined as: (date of first documented MMR - date of randomization + 1)/7.

Duration of MMR is defined for patients in the MMR Responder Set as the time between the date of the first documented MMR and the end date of MMR, i.e. the earliest date of confirmed loss of MMR, progression to accelerated phase (AP)/blast crisis (BC), or CML-related death.

Loss of MMR and progression to accelerated phase (AP)/blast crisis (BC) are defined in Appendix.

For patients for whom none of the events above is reported, the duration will be censored (see [Section 2.7.3](#)). The duration of MMR (in weeks) is calculated as: (end date or censoring date of MMR - date of first MMR + 1)/7.

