5.4 Efficacy variables

5.4.1 Molecular response

Scaling towards an international standard will be performed for all molecular results using laboratory specific conversion factors. In this process, the raw ratio between BCR-ABL and the control gene ABL is calculated and multiplied by the lab-specific conversion factor ([Branford and Hughes 2006]). Therefore, using the international unit, the BCR-ABL ratio will be presented in %. The MRDx assay using PAXgene™ Blood RNA tubes from MMD laboratory will be used in this study. The lab conversion factor for this assay was 1.1 until 1 June 2020 and 1 thereafter.

The BCR-ABL ratio in IS % is calculated by multiplying the raw BCR-ABL ratio with the lab-specific conversion factor and then by 100:

$$\text{BCR-ABL ratio (in \%)} = (\text{BCR-ABL} / \text{ABL}) * \text{conversion factor} * 100$$

The BCR-ABL ratio in IS% provided by the central laboratory will be use in the analyses. However, to calculate the fold change in BCR-ABL1/ABL used to derive the loss of MMR criteria, in case the BCR-ABL number of copies is reported as a 0 value and the patient doesn't have atypical transcript at baseline, then the value will be replaced by 1, and the BCR-ABL ratio will be calculated.

Molecular response is categorized as follows:

- 10% > BCR-ABL ratio
- 1% < BCR-ABL ratio ≤ 10%
- 0.1% < BCR-ABL ratio ≤ 1%
- 0.01% < BCR-ABL ratio ≤ 0.1%
- 0.0032% < BCR-ABL ratio ≤ 0.01%
- BCR-ABL ratio ≤ 0.0032%

Major molecular response (MMR)

Major molecular response (MMR) is defined as a value of ≤ 0.1% of BCR-ABL ratio on the IS. This endpoint corresponds to a ≥ 3 log reduction in BCR-ABL transcripts from a standardized baseline value for untreated CML patients which was established in the IRIS study (STI5710106). MMR will be considered as a binary variable with patients achieving MMR

grouped as ‘responders’ and patients not achieving MMR or patients with missing PCR evaluations grouped as ‘non-responders’.

Loss of MMR

Loss of MMR is defined as an increase in BCR-ABL1/ABL to $> 0.1\%$ by international scale (IS) in association with a ≥ 5 -fold rise in BCR-ABL1/ABL from the lowest value achieved up to that time point on study treatment and replicated by a second analysis of the same sample. Loss of MMR must be confirmed by a subsequent sample analysis within 4-6 weeks showing loss of MMR associated with a ≥ 5 -fold rise in BCR-ABL1/ABL from the lowest value achieved up to that time point on study treatment.

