If there is any assessment in between indicating a BCR-ABL ratio of $\leq 0.1\%$ or a < 5 -fold increase in BCR-ABL ratio from the lowest value achieved up to that time point on study treatment, then the initial indication of loss of MMR cannot be confirmed. However, an assessment indicating (unconfirmed) loss of MMR will be considered as confirmed loss of MMR if the patient had loss of CHR or loss of complete cytogenetic response (CCyR) after the achievement of MMR. CML-related death or progression to AP or BC will be considered as confirmed loss of MMR in any case (if they occurred on treatment) (given that the patient achieved prior MMR).

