5.4.3 Hematologic response

Loss of CHR

Loss of CHR is defined by meeting any of the following:

- WBC count > $20 \times 10^9/L$
- Platelet count $\geq 600 \times 10^9/L$
- Appearance of blasts or promyelocytes in peripheral blood
- Appearance of myelocytes + metamyelocytes $\geq 5\%$ in peripheral blood
- Progressive splenomegaly refractory to therapy (i.e. $\geq 5\text{cm}$ below left intercostal margin)

Loss of CHR must have led to treatment discontinuation because of lack of efficacy (based on the “End of Treatment Phase Disposition” eCRF or “End of Treatment Disposition” eCRF during the Treatment switch phase with Subject status=“lack of efficacy” and Reason of treatment failure = “After start of therapy, loss of CHR, CCyR or PCyR”).

In addition, CML-related death or progression to AP or BC will be considered as loss of CHR in any case (if they occurred on treatment).

Complete hematologic response (CHR)

CHR is defined when all of the following criteria are present at any assessment which is confirmed by another assessment at least after 4 weeks:

- White blood cells (WBC) count < $10 \times 10^9/L$
- Platelet count < $450 \times 10^9/L$

- Basophils < 5%
- No blasts and promyelocytes in peripheral blood
- Myelocytes + metamyelocytes < 5% in peripheral blood
- No evidence of extramedullary disease, including spleen and liver. As extramedullary disease is evaluated less frequently than hematology, the results of these evaluations are carried forward until the next assessment (unless extramedullary disease was not present at the current assessment but present at the next).

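### The loss-of-MMR definition (SAP 5.4.1) lets a later loss of CHR or CCyR confirm an old PCR signal, with no link in time and no exclusion of refuted signals, so duration of MMR can end too early

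*Combined protocol and SAP*

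**What the plan says.** The current text is SAP addendum 1.0 (14 October 2020). Section 5.4.1 reads the same in Amendment 3 (7 August 2020).

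- **What is a signal.** "Loss of MMR is defined as an increase in BCR-ABL1/ABL to" above 0.1% IS, with at least a 5-fold rise from the on-treatment nadir, "and replicated by a second analysis of the same sample" (5.4.1).
- **Ordinary confirmation.** "Loss of MMR must be confirmed by a subsequent sample analysis within 4-6 weeks showing" the same degree of loss (5.4.1).
- **Refutation.** If a PCR in between is at or below 0.1%, or shows less than a 5-fold rise, "then the initial indication of loss of MMR cannot be confirmed" (5.4.1).
- **Exception.** The next sentence, which opens with However, adds this: "an assessment indicating (unconfirmed) loss of MMR will be considered as confirmed loss of MMR if the patient had loss of CHR". Losing CCyR has the same effect. The only time condition is that this loss came after MMR was achieved.
- **What counts as loss of CHR or CCyR.** Under 5.4.2 and 5.4.3 the loss must have led to discontinuation for lack of efficacy. On-treatment events qualify separately: "CML-related death or progression to AP or BC will be considered as loss of CHR" (5.4.3), and 5.4.2 has the parallel rule for CCyR.
- **End of MMR.** "the earliest date of confirmed loss of MMR", or AP/BC, or CML-related death (2.7.1.1). Responders without an event are censored at their last on-treatment PCR (2.7.3).

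**The concern.** The refutation rule exists so that an isolated rise, contradicted by the next sample, does not count as a loss. The exception comes straight after it and can undo it. A signal that could not be confirmed is unconfirmed in the ordinary sense of the word, and the exception upgrades unconfirmed signals without asking why they stayed unconfirmed. It does not ask whether MMR was regained, how far apart the two events are, or even whether the loss of CHR or CCyR came after the signal.

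What the exception confirms is the PCR assessment itself. Since the earliest confirmed loss ends MMR, an event much later in follow-up can place the end of response on a date after which PCRs still showed MMR. The Kaplan-Meier curve and the proportions still in MMR at 24, 48, 72 and 96 weeks would then carry events at the wrong times. AP/BC and CML-related death are exposed in the same way: 2.7.1.1 gives them their own dates, but an old signal upgraded through the CHR or CCyR route would come first.

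**Working it through.** The plan gives no figure for duration of MMR or for loss events, so there is nothing to reproduce. The check traces the rule on a hypothetical patient.

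**Inputs**
- Target day of Week k is 7k + 1 (Section 2.1.1): Week 12 = 85, Week 36 = 253, Week 84 = 589, Week 96 = 673.
- Duration in weeks = (end date − date of first MMR + 1) / 7 (Section 2.7.1.1).
- Assumed course: first MMR at Week 12; PCR 0.6% at Week 36, replicated in the same sample; PCR 0.04% at Week 40; MMR through Week 84, the last on-treatment PCR; loss of CCyR with discontinuation for lack of efficacy at Week 96.

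**Does the Week 36 result qualify?** The nadir is at most 0.1%, so the rise is at least 0.6 / 0.1 = 6-fold, and the level exceeds 0.1%. It does. The Week 40 value of 0.04% then refutes it.

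**Duration under each reading**

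| Reading | Calculation | Weeks |
|---|---|---|
| Signal upgraded, dated at Week 36 | (253 − 85 + 1) / 7 | 24.1 |
| Signal stays refuted, censored at Week 84 PCR | (589 − 85 + 1) / 7 | 72.1 |
| Signal upgraded, dated at Week 96 loss | (673 − 85 + 1) / 7 | 84.1 |

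The middle row is a censoring because 2.7.1.1 does not list loss of CCyR as an end event in its own right. Dating at the signal shortens duration by 72.1 − 24.1 = 48 weeks or 84.1 − 24.1 = 60 weeks. The patient counts as lost before the 48- and 72-week time points, although both other readings have MMR continuing past them.

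**Range.** Against dating at the CHR/CCyR loss, the shortening equals the interval between signal and loss, whatever the date of first MMR. For a signal at Week 36:

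| CHR/CCyR loss at | Gap (weeks) | Gap (months, weeks × 7 / 30.4375) |
|---|---|---|
| Week 42 | 6 | 1.4 |
| Week 48 | 12 | 2.8 |
| Week 72 | 36 | 8.3 |
| Week 96 | 60 | 13.8 |

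**Size of the responder set.** It includes MMR at any time on study treatment (Section 2.2), so the Week 24 planning rates give too low a count: 0.35 × 148 + 0.15 × 74 = 62.9. On the Week 96 figures in Section 3.2 (bosutinib 30%; asciminib 50% to 53%, which are detectable values rather than forecasts), it is 0.50 × 148 + 0.30 × 74 = 96.2 to 0.53 × 148 + 0.30 × 74 = 100.6. How many of these would have both a refuted signal and a qualifying later loss cannot be derived.

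**The case against.** The best defence is that the exception was meant only to stand in for a missing 4-6-week sample, which is plausible when the qualifying loss ends treatment. The text does use different words for signals that cannot be confirmed and signals that are unconfirmed. Section 4, in listing changes to this definition, mentions only that confirmation of CHR and CCyR was dropped; it announces no power to revive refuted signals. This may well be the intent, but the sentence does not say so, and its position after the refutation rule points the other way.

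Second, no date is stated for a loss confirmed by this route. If it is dated at the loss of CHR or CCyR, nothing is shortened relative to that date. That stands as a limit on the size. The silence still leaves two programmers free to produce different end dates.

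Third, the affected group is narrow. Not every PCR rise qualifies, and the CHR or CCyR loss must have led to discontinuation for lack of efficacy or be an on-treatment AP/BC or CML-related death. Aspirates for cytogenetics are planned only while MMR has not been achieved (2.7.1.2), so the CCyR route will seldom be open to a patient in sustained MMR. All of this stands; it reduces the number of cases but not the possible error in each.

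A reader might also infer that the Week 24 or Week 96 MMR rate is at risk. If the upgraded signal counted as treatment failure, Section 2.1.1 would apply: "The efficacy assessments collected post-treatment failure, post-EoT or post S-EoT visit are not included in any efficacy analyses", with OS and PFS excepted, and a responder could be reversed by a later event. The documents do not support this. The criterion in 5.4.4 asks for a confirmed loss on two tests in a row, and a refuted signal is one positive test followed by a negative one.

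**Conclusion.** The concern holds as a defect in a derivation rule. Section 5.4.1 sets no link in time between a qualifying unconfirmed signal and the loss of CHR or CCyR that confirms it, and it does not keep refuted signals refuted. Read literally with 2.7.1.1, duration of MMR can end at a transient signal: 24.1 weeks against 72.1 or 84.1 weeks in the example, which rests on an assumed visit course and on dating at the signal.

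The consequence is limited. Probably few patients are affected. Duration of MMR is a secondary endpoint summarised by Kaplan-Meier, with no confirmatory testing (2.7.2), and it is repeated in the Switch Analysis Set (2.14). It would go too far to say that any PCR rise is turned into a loss, that durations will be months too short, or that the primary or key secondary endpoint is affected.

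**What to change.** Replace the exception in 5.4.1 with a rule that states four things:

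1. A signal followed by a PCR at or below 0.1%, or with less than a 5-fold rise from nadir, stays refuted and is never upgraded.
2. An unconfirmed signal counts as confirmed by loss of CHR or CCyR only if that loss is documented on or after the signal, with no refuting PCR in between.
3. A loss confirmed in this way is dated at that unrefuted signal.
4. AP/BC and CML-related death keep their own dates.

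Dating a refuted signal at the later loss of CHR or CCyR would not be a clean alternative. A patient with the same loss and no earlier signal has no MMR-loss event from it, so the refuted signal would still decide whether an event is counted. Under the rule above, the example patient is censored at the Week 84 PCR, at 72.1 weeks.

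The cost is one sentence of SAP text and one extra condition in the derivation program. No new data are needed.

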5.4.2 Cytogenetic response

Cytogenetic response will be based on the percentage of Ph⁺ metaphases in the bone marrow. Cytogenetic evaluations will be considered for response assessment only if the number of metaphases examined is ≥ 20 in each bone marrow sample. As per protocol, fluorescent *in-situ* hybridization (FISH) assessments will not be considered for any evaluation of cytogenetic response during treatment.

Cytogenetic response is categorized as follows (a review of a minimum of 20 metaphases is required):

- Complete response (CCyR): 0% Philadelphia chromosome positive (Ph⁺) metaphases
- Partial response (PCyR): >0 to 35% Ph⁺ metaphases
- Major response (MCyR = CCyR + PCyR): 0 to 35% Ph⁺ metaphases
- Minor response (mCyR): >35 to 65% Ph⁺ metaphases
- Minimal response: >65 to 95% Ph⁺ metaphases
- None: >95 to 100% Ph⁺ metaphases.

If bone marrow aspirate blast percentage is provided as ‘ $<X$ ’ (i.e. below limit of detection), the numeric value is set to X for summary tables. In the listing ‘ $<X$ ’ will be presented.

Complete cytogenetic response (CCyR)

CCyR is defined as a value of 0% Ph⁺ metaphases in bone marrow.

CCyR will be considered as a binary variable with patients achieving CCyR grouped as ‘responders’ and patients not achieving CCyR, patients with missing cytogenetic evaluations grouped as ‘non-responders’.

Loss of CCyR

Loss of CCyR is defined as an increase in the Ph+ bone marrow cells to > 0%.

Loss of CCyR must have led to treatment discontinuation because of lack of efficacy (based on the “End of Treatment Phase Disposition” eCRF or “End of Treatment Disposition” eCRF during the Treatment switch phase with Subject status=“lack of efficacy” and Reason of treatment failure = “After start of therapy, loss of CHR, CCyR or PCyR”).

In addition, CML-related death or progression to AP or BC will be considered as loss of CCyR in any case (if they occurred on treatment).

Major cytogenetic response (MCyR)

MCyR is defined as a value of 0% to 35% Ph+ metaphases in bone marrow.

MCyR will be considered as a binary variable with patients achieving MCyR grouped as ‘responders’ and patients not achieving MCyR, patients with missing cytogenetic evaluations grouped as ‘non-responders’.

Loss of MCyR is defined as an increase in the Ph+ bone marrow cells to > 35%. For patients with response = PCyR, this would constitute loss of PCyR.

CML-related death or progression to AP or BC will be considered as confirmed loss of MCyR in any case (if they occurred on treatment).

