1.1 Study design

This is a randomized, Phase III, open-label, active-controlled, multi-center study comparing safety and efficacy of asciminib to bosutinib in patients with CML-CP, previously treated with 2 or more tyrosine kinase inhibitors (Figure 1-1). Approximately 220 patients will be randomized to one of the following treatment arms in 2:1 ratio:

- asciminib 40 mg BID
- Bosutinib 500 mg QD

Randomization will be stratified by the following factor: cytogenetic response status (with or without major cytogenetic response).

Figure 1-1 Schematic of Study Design

Patients with documented treatment failure (as per the 2013 ELN guidelines, [Baccarani et al 2013](#)) while on bosutinib treatment will have the option to switch to asciminib treatment within

96 weeks after the last patient has been randomized on study. The patients who switch to asciminib will be able to receive asciminib up to the end of study treatment (EOsT) period.

Patients will be treated up to the EOsT defined as up to 96 weeks after the last patient received the first study dose (LPFT) or up to 48 weeks after the last patient has switched to asciminib treatment whichever is longer, if they do not discontinue study treatment earlier. After the EOsT, the assigned study treatment will be made available to patients who in the opinion of the investigators are still deriving clinical benefit. This may be outside of this study through alternative options including, but not limited to, an expanded access/compassionate use/managed access program or access to commercial supplies in applicable countries.

Major Molecular Response (MMR) rate at 24 weeks is the primary endpoint in this study. MMR rate at 96 weeks is the key secondary endpoint.

Four analyses are planned for this study, including the 24-week primary analysis, the 96-week analysis, the End-of-Study-Treatment (EOsT) analysis, and Progression-Free survival/Overall survival (PFS/OS) update analysis. The timing when those analyses are conducted is summarized in Section 2.1.

No formal interim efficacy analysis is planned in this study. A data monitoring committee (DMC) will monitor unblinded safety data approximately 6 months after the first randomized patient has started study treatment. Subsequent reviews will be conducted approximately every 6 months and when needed thereafter (ie. if significant safety findings are noted) until the primary analysis.

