5.4.4 Treatment Failure

The following events will constitute 'treatment failure', and are based on the ELN criteria ([Baccarani et al 2013](#)) defining failure of a second line treatment adapted to include discontinuation of randomized treatment as an event:

- No CHR or > 95% Ph+ metaphases at three months after initiation of therapy or thereafter
- BCR-ABL1 ratio > 10% IS and/or > 65% Ph+ metaphases at six months after initiation of therapy or thereafter
- BCR-ABL1 ratio > 10% IS and/or > 35% Ph+ metaphases at 12 months after initiation of therapy or thereafter
- Loss of CHR, CCyR or PCyR at any time after initiation of therapy
- Detection of new BCR-ABL1 mutations which potentially cause resistance to study treatment (T315I and V299L), at any time after initiation of therapy
- Confirmed loss of MMR in 2 consecutive tests
- New clonal chromosome abnormalities in Ph+ cells: CCA/Ph+: at any time after initiation of therapy

- Discontinuation from randomized treatment for any reason* (Note that Reason for treatment discontinuation="completed" doesn't indicate a premature treatment discontinuation)

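### A laboratory-defined loss of CCyR or CHR counts only if treatment was then stopped and coded for it, so duration of CCyR is overstated whenever such a stop does not follow

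*Combined protocol and SAP*

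**What the plan says.** Section numbers refer to the SAP with addendum 1.0 (14-Oct-2020). Amendment 3.0 (7-Aug-2020) reads the same on these points.

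- **Section 5.4.2, CCyR.** "Loss of CCyR is defined as an increase in the Ph+ bone marrow cells to > 0" per cent. The SAP then adds: "Loss of CCyR must have led to treatment discontinuation because of lack of efficacy". The stop is identified from the disposition eCRF, which must show lack of efficacy and, as the failure reason, loss of hematologic or cytogenetic response. There is one exception, for events on treatment: "CML-related death or progression to AP or BC will be considered as loss of CCyR in any case".
- **Section 5.4.3, CHR.** Any one of several blood or spleen findings defines the loss, but "Loss of CHR must have led to treatment discontinuation because of lack of efficacy". The same exception applies.
- **Section 5.4.2, MCyR.** "Loss of MCyR is defined as an increase in the Ph+ bone marrow cells to > 35" per cent. For a patient in PCyR this is loss of PCyR. Nothing is said about stopping treatment.
- **Section 5.4.4, treatment failure.** Loss of any of these three responses is a failure event. So is "Discontinuation from randomized treatment for any reason". So is "No CHR or > 95% Ph+ metaphases at three months after initiation of therapy or thereafter".
- **Sections 2.7.1.2, 2.7.2 and 2.7.3, duration of CCyR.** It ends at loss of CCyR, AP/BC or CML-related death. Otherwise it is censored at the later of the last on-treatment cytogenetic assessment and the last on-treatment PCR showing MMR. Kaplan-Meier proportions still in CCyR are planned per arm at 24, 48, 72 and 96 weeks.
- **Section 1.1.** The trial is open-label. Patients with documented failure "while on bosutinib treatment will have the option to switch to asciminib treatment". No matching option is described for the asciminib arm.
- **Document history and Section 4.** The CCyR condition came in with amendment 3.0, before the primary database lock, and the only stated reason is alignment with loss of CHR. Section 4 mentions the CHR definition but not this change.

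**The concern.** Loss of response is a measured event, but here it becomes an event only through a later decision by an unblinded investigator and the code chosen on a form. Two things are at stake.

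The first is the meaning of duration of CCyR. A patient whose marrow shows Ph+ metaphases is no longer in CCyR at that visit under Section 2.7.1.2, yet can stay in the Kaplan-Meier proportion described as still in CCyR. This needs no difference between the arms.

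The second is comparability. Recording failure opens a switch for bosutinib patients only, so the readiness to stop and code a loss may differ by arm.

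The definitions also reach further. Under Section 5.4.1, loss of CHR or CCyR can turn an unconfirmed loss of MMR into a confirmed one, so duration of MMR inherits the condition. Failure status before week 24 also makes a patient a non-responder on the primary endpoint (Section 2.5.1).

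**Working it through.** The plan gives no figure for loss of response or for duration of CCyR, so there is none to reproduce. The sample size of 222 is not affected.

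**1. One patient traced through the rules.** A patient is in CCyR at week 24. At week 48, 2 of 20 metaphases are Ph+ (10%), and the patient stays on treatment.
- Response category at week 48 (Section 2.7.1.2): PCyR, so not CCyR.
- Loss of CCyR (Section 5.4.2): none, because no stop followed.
- Duration of CCyR (Section 2.7.3): no event. The patient is censored at the last cytogenetic assessment or last PCR in MMR, so at week 48 or later.

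The patient is censored no earlier than the sample that shows the loss. The same holds if the patient stops under a different reason code. Section 5.5.1 has a category for patients ongoing with treatment failure, so the SAP itself expects some to continue after failing.

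**2. Contribution to treatment failure.** A laboratory-defined loss of CCyR or CHR counts only with a discontinuation. Any discontinuation other than completion is already a failure. The number of additional failed patients from these laboratory losses is therefore 0. If the loss is dated at the sample, it can only bring the failure date forward.

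**3. Uneven treatment of similar results.** Read literally, a patient in PCyR who goes from 30% to 40% Ph+ has lost PCyR. A patient in CCyR who goes from 0% to 40% and stays on treatment has lost neither CCyR (no stop) nor PCyR (not in PCyR). Only the time-based Ph+ limits in Section 5.4.4 could then register failure, and these do not end CCyR for its duration.

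**4. Size within one arm (assumed inputs).** Let L be the true share losing CCyR by a given time, and s the share of those losses followed by a stop with the required code. If uncounted patients stay in follow-up, the apparent proportion still in CCyR is 1 − s × L. For L = 20%:
- s = 1: 1 − 1 × 0.20 = 80% (the true value)
- s = 0.8: 1 − 0.8 × 0.20 = 84%
- s = 0.5: 1 − 0.5 × 0.20 = 90%

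If uncounted patients are instead censored at the marrow that showed the loss, the formula is (1 − L)^s. For s = 0.5 that gives 0.80^0.5 = 0.894, or 89%. The exact point of censoring hardly matters.

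**5. Size between arms (assumed inputs).** With the same true loss in both arms, the apparent proportion still in CCyR, asciminib versus bosutinib, is 1 − s × L in each arm:

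| True loss L | s = 0.7 v 0.9 | s = 0.5 v 0.9 | s = 0.3 v 0.9 |
|---|---|---|---|
| 10% | 93% v 91% | 95% v 91% | 97% v 91% |
| 20% | 86% v 82% | 90% v 82% | 94% v 82% |
| 40% | 72% v 64% | 80% v 64% | 88% v 64% |

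A simulation with 24-weekly assessments and staggered follow-up gave the same values to within 0.1 percentage point for the 0.5 v 0.9 and 0.3 v 0.9 pairs at 20% and 40% loss. With s = 1 in both arms there is no distortion.

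**6. The two CHR rules side by side.** CHR requires, among other things, WBC below 10 and platelets below 450 (×10⁹/L). Loss of CHR requires, for example, WBC above 20 or platelets of at least 600, plus a coded stop. Take a WBC of 15 after month three in a patient previously in CHR. If the no-CHR bullet applies at every later visit, this is failure. If that bullet means CHR never achieved, it is not failure, and under Section 5.4.3 it is not loss of CHR either. The text does not settle which reading applies.

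**The case against.** The best defence of the condition is that it screens out noise. Section 4 says that confirmation of CHR and CCyR was not mandated and not done in practice. Cytogenetic time points are 24 weeks apart, and a single Ph+ metaphase in 20 would otherwise end a response. That is a reason for care. It does not make a stopping decision a confirmation of a laboratory value, and it does not justify counting a patient with many Ph+ metaphases as still in CCyR.

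A second defence is that the effect is bounded. Efficacy data stop at treatment failure (Section 2.1.1), and the Ph+ limits in Section 5.4.4 (above 95% from three months, 65% from six, 35% from twelve) catch larger losses. This stands as a limit on how long such patients are followed and as partial protection for time to treatment failure. It does not create a loss event in duration of CCyR.

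Three stronger readings are tempting, and the documents do not support them.
- A reader might infer that the rule demonstrably favours asciminib, with a hazard ratio near 0.50/0.90 = 0.56. The shares behind that ratio are invented, and no hazard ratio is planned for duration of CCyR. The current protocol's discontinuation sections are not in the part available. If they require stopping at loss of response in both arms, s moves towards 1 and the effect shrinks.
- A reader might infer that the whole loss-of-response bullet in Section 5.4.4 is redundant. It is not: on-treatment AP/BC counts without a stop, and loss of PCyR carries no condition.
- A reader might infer that an objective central reading is being overridden. Only the BCR-ABL ratio is described as coming from the central laboratory. Marrow results are described as eCRF data.

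**Conclusion.** The rule as written overstates duration of CCyR in any arm where a patient with Ph+ above 0% stays on treatment or stops under another code. That conclusion rests on the text alone. Its size depends on how often this happens, which the documents do not say; on the assumed inputs, 80% truly in CCyR would appear as 84% to 90%.

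A difference between arms, in asciminib's favour, is plausible given open-label treatment and the one-way switch. Its existence and size cannot be established here; the assumed cases give gaps of 2 to 24 percentage points.

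The consequences are limited. Duration of CCyR is a non-key secondary endpoint without confirmatory testing (Section 2.7.2). The primary and key secondary endpoints also require BCR-ABL of 0.1% or less on treatment, so the effect there is probably small. The overlap between the no-CHR bullet and loss of CHR is an ambiguity to resolve, not a demonstrated error in the primary result. The change is worth making because it is cheap.

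**What to change.** 1. For duration of CCyR, derive loss of CCyR from the cytogenetic result alone: Ph+ above 0% on at least 20 metaphases, dated at the sample. Derive loss of CHR from the findings already listed in Section 5.4.3. State which version Sections 5.4.1 and 5.4.4 use.
2. Report the discontinuation-linked version alongside as a sensitivity analysis.
3. Tabulate by arm the patients with Ph+ above 0% who were not counted as losses, split by still on treatment and by recorded reason for stopping. This shows directly whether s differs between arms.
4. List the change to loss of CCyR in Section 4.
5. For the endpoint derivation, reconcile the no-CHR bullet with the loss-of-CHR definition, so that one rule decides failure status after three months.

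The cost is SAP wording and reprogramming from collected data. Addendum 1.0 follows the primary database lock, so any re-run of the week-24 results should be labelled post hoc.

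The downside is that single unconfirmed values, such as 1 of 20 metaphases, may add some events. Confirmation can be applied only where a later sample happens to exist. Because marrow is not required once a patient is in MMR, losses are seen only where an aspirate was done.
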